4.7 Duration of Metformin Therapy

The planned duration of metformin therapy is 12 months. Metformin treatment will be discontinued early in the following scenarios:

- Progression of disease, as defined by CAH progression to invasive adenocarcinoma or grade 1 EC progression to grade 2 or 3 EC, at any of the standard of care biopsies at 3, 6, and 9 months. In any of these cases, metformin will be discontinued within 3 days of results of the biopsy.
- Unacceptable toxicity as defined by a single grade 3 or higher GI disturbance attributed to metformin, a single grade 4 or higher hypoglycemia episode, 2 or more grade 2 toxicities attributed to metformin, or requirement for a dose below 850 mg once daily.

Response to therapy will be assessed at 3-month intervals. As per standard of care, endometrial biopsies will be performed every 3 months (+/- 2 weeks) to assess histology and grade to determine response. This will be the basis of whether therapy should continue. If the 3 month biopsy demonstrates disease progression, the patient will be removed from protocol directed treatment and followed-up per protocol, and treatment decisions will be at the discretion of the treating physician. Otherwise, therapy will continue through 6 months. If the 6-month or 9-month biopsy demonstrates complete response (complete disease regression) or partial response (partial disease regression), metformin will be continued until 12 months of total therapy is given. If the 6-month or 9-month biopsy demonstrates stable disease, continuation of metformin on study will be at the discretion of the treating physician. Please see the schema (section 4.1) for clarity.

In addition, treatment will be stopped in the setting of:

- Inter-current illness that prevents further administration of treatment
- Pregnancy
- Patient decides to withdraw from study treatment, **OR**
- General or specific changes in the patient's condition render the patient unacceptable for further treatment in the judgment of the investigator.

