4.8 Duration of Follow Up

Patients will be followed until their final study encounter (this may be a clinic visit, or phone call), which will occur within 30 days of their final endometrial biopsy while on metformin. Metformin is to be stopped the day of the 12-month endometrial biopsy, or the day on which the results of prior biopsies are known, if they indicate disease progression. In the case of ongoing adverse events/serious adverse event, patients will be followed to resolution of the event.

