6.5 Final Study Encounter

Metformin is to be stopped the day of the 12-month endometrial biopsy, or the day on which the results of prior biopsies are known, if they indicate disease progression. In the case of ongoing adverse events/serious adverse event, patients will be followed to resolution of the event. After completion of metformin treatment, patients may return to clinic as per scheduled with their primary provider. The final study encounter will be within 30 days of the final endometrial biopsy.

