6.6 Early Termination/Study Withdrawal Visit

If early termination of the study occurs (i.e., prior to 12 months), the patient will be asked to have serum and urine collected, and their standard of care every 3 month endometrial biopsy will be performed as scheduled by their physician as per routine care. No other evaluations will be needed in the event of early termination. Subjects may withdraw voluntarily from participation in the study at any time (see section 4.10). Subjects may also withdraw voluntarily from receiving the study intervention for any reason.

If voluntary withdrawal occurs due to an adverse event, the subject will be given appropriate care under medical supervision until the symptoms of any adverse event resolve or the subject's condition becomes stable.

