7.2 Documentation of non-serious AEs or SARs

For non-serious AEs or SARs, documentation must begin from day 1 of study treatment and continue through the 30 day follow-up period after treatment is discontinued.

Collected information should be recorded in the Case Report Forms (CRF) for that patient. Please include a description of the event, its severity or toxicity grade, onset and resolved dates (if applicable), and the relationship to the study drug. Documentation should occur at least monthly.

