7.3 SAEs or Serious SARs

7.3.1 Timing

After informed consent but prior to initiation of study medications, only SAEs caused by a protocol-mandated intervention will be collected (e.g. SAEs related to invasive procedures such as biopsies, medication washout, or no treatment run-in).

For any other experience or condition that meets the definition of an SAE or a serious SAR, recording of the event must begin from day 1 of study treatment and continue through the 30 day follow-up period after treatment is discontinued.

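### AE and SAE recording ends 30 days after metformin stops, but the final study encounter is timed from a biopsy, so no passage clearly dates an AE contact at the end of that window

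*Combined protocol and SAP*

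**What the plan says.** **Recording window.** Non-serious AEs are recorded from day 1 of treatment and "continue through the 30 day follow-up period after treatment is discontinued" (Section 7.2). For SAEs, "recording of the event must begin from day 1 of study treatment and continue through the 30 day follow-up period after treatment is discontinued" (Section 7.3.1).

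**Final study encounter.** Section 4.8 follows patients until this encounter, by visit or phone, "which will occur within 30 days of their final endometrial biopsy while on metformin". Footnote 2 to the Time and Events Table gives the same rule. Section 6.5 is looser: "The final study encounter will be within 30 days of the final endometrial biopsy". It does not restrict the biopsy to one taken on drug.

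**When metformin stops.** For completers, "Metformin is to be stopped the day of the 12-month endometrial biopsy". After progression it stops once biopsy results are known. Section 4.7 also lists reasons unconnected with any biopsy: toxicity (one trigger is a single severe GI event attributed to metformin), intercurrent illness, pregnancy and the patient's own decision.

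**Other contact.** Section 4.4 and footnote 7 give toxicity assessments at 30-day intervals with no stated end, and Section 7.2 asks for documentation at least monthly. Section 6.4.2 puts the same calls under a heading that confines them to the time on metformin. For early termination, Section 6.6 asks for serum, urine and routine-care biopsies, then says: "No other evaluations will be needed in the event of early termination". Footnote 2 adds follow-up until treatment-related events have resolved or returned to baseline.

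**The concern.** The obligation to record is counted from the last dose, and the contact that ends follow-up is counted from a biopsy. The two clocks start together only when metformin stops on a biopsy day. Otherwise the final encounter can fall due before the recording window closes, or even before the last dose.

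Describing safety is a secondary objective (2.2.4). If nobody is clearly required to ask about new events near day 30, what is recorded after stopping depends on whether the patient volunteers it and on how each site reads the schedule. In a multi-center study, that makes the length of post-treatment observation vary by site and by reason for stopping.

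**Working it through.** The plan states no figure that depends on this timing, so there is none to reproduce. The check is date arithmetic.

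**Inputs**
- Recording window: 30 days after discontinuation (7.2, 7.3.1).
- Encounter deadline: 30 days after the last on-metformin biopsy (4.8, footnote 2).
- Biopsy spacing: 3 months, each biopsy +/- 2 weeks (4.7). Nominal gap 3 x 365.25/12 = 91.3 days. With adjacent biopsies shifted in opposite directions, 91.3 - 28 = 63.3 to 91.3 + 28 = 119.3 days.

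**Days of the window after the deadline**

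Call the last on-metformin biopsy day 0 and the stop day t. The encounter is due by day 30, and the window runs from day t to day t + 30. The days of the window after the deadline are (t + 30) - max(30, t) = min(30, t).

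| t (days) | Days after the deadline | Deadline relative to last dose |
|---|---|---|
| 0 | 0 | 30 days after |
| 7 | 7 | 23 days after |
| 15 | 15 | 15 days after |
| 30 | 30 | same day |
| 45 | 30 | 15 days before |
| 61 | 30 | 31 days before |

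The last row is a woman with a month-3 biopsy who stops at about month 5. These are minimum figures, because the encounter may be held before its deadline.

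**Special cases**
- Stop before the month-3 biopsy: there is no on-metformin biopsy, so Section 4.8 gives no date.
- Stop for progression: t equals the time taken for results. The documents do not state that time; if it were 7 days, at least 7 days of the window would fall after the deadline.
- Completer: t = 0, so the clocks agree, but the 30 days is only an upper limit. A call on day 7 would leave 30 - 7 = 23 days of the window after it.

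**Illustrative share of stops after the deadline**

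Assume stop dates spread evenly over a biopsy gap G. The share falling after the deadline is (G - 30)/G:
- G = 91.3: 61.3/91.3 = 67%
- G = 63.3: 33.3/63.3 = 53%
- G = 119.3: 89.3/119.3 = 75%

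**Number of women**

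The stopping rule in Section 8.2 treats a 25% discontinuation rate for toxicity as acceptable: 0.25 x 32 = 8 women at planned accrual. The documents do not say how many would stop between biopsies.

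**Section 6.5 taken alone**

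Routine biopsies continue after early termination, so a later off-drug biopsy could set the date. The month-5 stopper's month-6 biopsy falls about 30 days after her last dose, and an encounter after it would cover the window. This is not guaranteed. If the next biopsy comes 7 days after stopping and is taken as the final one, the encounter may fall anywhere from 7 to 37 days after the last dose.

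**The case against.** The strongest answer is that the protocol already provides contact after stopping. Section 4.4 and footnote 7 set 30-day assessments without ending them at discontinuation, Section 7.2 wants documentation at least monthly, and Section 6.6 and the Time and Events Table provide an early-termination visit. On that reading, a call falls inside the 30-day window.

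Much of this stands. A reader might infer that early stoppers have no scheduled contact, or that the final encounter is the only post-treatment contact. The documents support neither. The early-termination visit exists, though undated, and the 30-day calls may continue. The empty AE Assessment row of the table proves nothing, since it shows no marks even during treatment and its markings were probably lost in text extraction.

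A reader might also infer that under-capture is worst in women who stop for toxicity. The documents do not show that. Ongoing events are followed to resolution (4.8), footnote 2 follows treatment-related events, and Section 6.6 provides supervised care after withdrawal for an adverse event.

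It can fairly be added that the biopsy-based deadline may not have been written with between-biopsy stops in mind, and that even spreading of stop dates has no source in the documents.

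The objection does not remove the conflict. Section 6.4.2 confines the calls to treatment, and Section 6.6 says nothing further is needed. Following known treatment-related events to resolution sets no dated contact to find new ones, while Section 7.1.1 defines AEs regardless of cause. A monthly documentation rule does not name a contact.

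**Conclusion.** The concern holds as a mismatch of timing rules. The final encounter cannot be relied on to cover the 30-day AE/SAE window, and the remaining passages disagree on whether anything else does. For a stop between biopsies, at least min(30, t) days of the window lie after the encounter deadline under Section 4.8. Stops before month 3 have no date under that section, and completers may be contacted early.

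The 67% (53% to 75%) is an illustration resting on evenly spread stop dates and on the wording of Section 4.8 rather than 6.5. It counts passed deadlines, and nothing in the documents allows a count of missed events. The supported consequence is that post-treatment AEs may be incompletely and unevenly captured across sites. The primary CR test does not depend on this. The change is worth making because it is cheap, not because the trial's main conclusion is at risk.

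**What to change.** In Sections 4.8 and 6.5 and footnote 2, time the existing final study encounter from the last metformin dose: a phone call or visit at or shortly after day 30, with AE and SAE review, whatever the reason for stopping. State the permitted tolerance. Then reconcile Sections 4.4, 6.4.2 and 6.6 and footnote 7 with it, saying whether the 30-day calls continue after stopping and making Section 6.6 refer to this contact. For women who stop therapy early, the contact would rest on the agreement to further assessments that Section 4.9 already seeks.

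The cost is protocol wording, a changed encounter date for some women, and one dated phone contact for early stoppers. No change to treatment, biopsies or the efficacy analysis is involved.

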7.3 SAEs or Serious SARs

7.3.1 Timing

After informed consent but prior to initiation of study medications, only SAEs caused by a protocol-mandated intervention will be collected (e.g. SAEs related to invasive procedures such as biopsies, medication washout, or no treatment run-in).

For any other experience or condition that meets the definition of an SAE or a serious SAR, recording of the event must begin from day 1 of study treatment and continue through the 30 day follow-up period after treatment is discontinued.

7.3.2 Documentation and Notification

These events (SAEs or Serious SARs) must be recorded in the SAE console within Oncore™ for that patient within 24 hours of learning of its occurrence.

7.3.3 Reporting

IRB Reporting Requirements:

- UNC will submit an aggregated list of all SAEs to the UNC IRB annually at the time of study renewal according to the UNC IRB policies and procedures.
- The UNC-IRB will be notified of all SAEs that qualify as an Unanticipated Problem as per the UNC IRB Policies using the IRB's web-based reporting system (see section 9.5.3) within 7 days of the Investigator becoming aware of the problem.
- For affiliate sites using a local IRB of record, please submit adverse events per local IRB policy.

- For affiliate sites relying on the UNC-IRB, an aggregated list of all SAEs will be submitted to the UNC IRB annually at the time of study renewal according to the UNC IRB policies and procedures. In addition, any SAEs that qualify as an Unanticipated Problem will be entered into Oncore and reported to the UNC IRB by the UNCCN Project Manager using the IRB's web-based reporting system (see section 9.5.3) within 7 days of the Investigator becoming aware of the problem.

Pregnancy

Pregnancies (including a positive pregnancy test regardless of age or disease state) of a female subject occurring while the subject is on study should be recorded as SAEs. The patient is to be discontinued immediately from the study. The female subject should be referred to an obstetrician-gynecologist, preferably one experienced in reproductive toxicity for further evaluation and counseling.

The Investigator will follow the female subject until completion of the pregnancy, and must document the outcome of the pregnancy (either normal or abnormal outcome). If the outcome of the pregnancy was abnormal (e.g., spontaneous or therapeutic abortion), the Investigator should report the abnormal outcome as an AE. If the abnormal outcome meets any of the serious criteria, it must be reported as an SAE.

7.4 Data and Safety Monitoring Plan

The Principal Investigator will provide continuous monitoring of patient safety in this trial with periodic reporting to the Data and Safety Monitoring Committee (DSMC).

Meetings/teleconferences will be held at a frequency dependent on study accrual, and in consultation with the study Biostatistician. These meetings will include the investigators as well as protocol nurses, clinical research associates, regulatory associates, data managers, biostatisticians, and any other relevant personnel the principal investigators may deem appropriate. At these meetings, the research team will discuss all issues relevant to study progress, including enrollment, safety, regulatory issues, and data collection.

The team will produce summaries or minutes of these meetings. These summaries will be available for inspection when requested by any of the regulatory bodies charged with the safety of human subjects and the integrity of data including, but not limited to, the oversight (Office of Human Research Ethics (OHRE) Biomedical IRB, the Oncology Protocol Review Committee (PRC) or the North Carolina TraCS Institute Data and Safety Monitoring Board (DSMB).

The UNC LCCC Data and Safety Monitoring Committee (DSMC) will review the study on a regular (quarterly to annually) basis, with the frequency of review based on risk and complexity as determined by the UNC Protocol Review Committee. The UNC PI will be responsible for submitting the following

information for review: 1) safety and accrual data including the number of patients treated; 2) significant developments reported in the literature that may affect the safety of participants or the ethics of the study; 3) preliminary response data; and 4) summaries of team meetings that have occurred since the last report. Findings of the DSMC review will be disseminated by memo to the UNC PI, PRC, and the UNC IRB and DSMB.

8.0 STATISTICAL CONSIDERATIONS

8.1 Study Design

This is an open label, single-arm, multi-center study of metformin in addition to the LR-IUD for the treatment of non-surgical patients with CAH and grade 1 EC. We hypothesize that metformin + LR-IUD will result in a CR rate at 6 months that is significantly higher than 50%.

8.2 Sample Size, Stopping Rule, and Accrual

The goal accrual is 32 patients (16 CAH, 16 EC) and we expect to enroll 1-2 patients/per month. Our power calculation and analysis will be based on 30 patients, assuming early discontinuation of 2 participants prior to 3 months of treatment. We estimate 18 months to complete accrual.

The primary objective of this study is to compare the CR rate at 6 months to a rate of 50% (the 50% is based on results reported in the meta-analysis referenced earlier, and because a response rate significantly greater than this will be considered clinically meaningful by the investigators). With a combined sample size of 30 evaluable patients with either CAH or grade 1 EC, and assuming a null CR rate of 50% and an alternative of 75%, we will have 80% power to conclude that the CR rate at 6 months is significantly higher than 50% using an exact test for a single proportion with a two-sided α of 0.05. Furthermore, the exact 95% confidence interval for the CR rate at 6 months will have a maximum width of 0.374. This means that the CR rate will be estimated within at least 18.7%. CAH and grade 1 EC represent a spectrum of neoplasia, which is why the two groups are being combined for the primary objective. The CR rate at 6 months will be estimated separately in the CAH and EC groups as a secondary objective.

Sequential boundaries will be used to suspend the trial if excessive toxicity is seen that requires discontinuation of metformin. If the study reaches a stopping boundary, it may be terminated by the PI, or submitted to the DSMC with a description of the toxicities and a rationale for why the study should be continued. At the patient level, metformin will be discontinued if a patient experiences: (1) a single grade 3 or higher metformin-related GI disturbance or grade 4 or higher hypoglycemic episode, or (2) two or more grade 2 side effects considered related to metformin therapy, or (3) if the patient requires a dose less than 850mg once daily. The accrual will be halted if the number of patients discontinuing metformin for one of the reasons above is equal to or exceeds b_n out of n patients who have been followed for toxicity for 3 months. This is a Pocock type stopping

boundary that assumes that a metformin discontinuation rate of 0.25 is acceptable, but anything $>25\%$ is unacceptable. If the true toxicity rate is equal to 0.25, the probability of crossing the boundary is 0.05.

Stopping Rule

Number of Patients, n	1	2	3	4	5	6	7	8	9	10	11	12	13	14	15	16	17	18	19	20
Boundary, b_n	-	-	-	4	5	5	5	6	6	7	7	7	8	8	9	9	9	10	10	10
Number of Patients, n	21	22	23	24	25	26	27	28	29	30	31	32	33	34	35	36	37	38	39	40
Boundary, b_n	11	11	11	12	12	12	13	13	14	14	14	15								

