3.2.9 Pregnant or lactating

3.2.10 Recent (< 30 days) active, documented, cervical infection

4.0 TREATMENT PLAN

4.1 Schema

This is an open-label, single-arm, multi-center, study of the addition of metformin to the LR-IUD for treatment of non-surgical patients with CAH and grade 1 EC. While patients will be enrolled prior to dilation and curettage (D&C) and placement of the LR-IUD, both are standard of care, and will not be impacted by enrollment into the study.

Oral metformin therapy will be started within 1 week of LR-IUD placement and continued for 12 months unless disease progression occurs or the patient develops intolerance.

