4.2 Dilation and Curettage (D&C)

As part of standard of care in treating CAH and EC with non-surgical progestin therapy, patients will undergo a D&C procedure for definitive diagnosis and therapeutic effect. During this procedure, the LR-IUD is placed. D&C is a safe, outpatient procedure that will be performed by a gynecologic oncology attending, fellow, or resident. In this procedure, the uterine lining tissue is removed with standard curette instruments. The main risk of this procedure is uterine perforation, which occurs at a rate of 1-2%. D&C would be performed regardless of study enrollment, and is not considered part of the current study. However, confirmation of CAH or EC will not be made, and therefore metformin will not be started, until after results of the D&C are read by the PI. This will occur within 3 days of receipt of the results and 7 days of the procedure and the patient will be informed that they can then initiate metformin. If a patient's provider does not feel

that they require a D&C procedure, the LR-IUD may be placed in clinic. The patient will undergo screening and pre-treatment testing at this time or the visit prior to the LR-IUD placement and will start the metformin within 30 days of IUD placement. Note that screening must occur within 30 days of starting treatment.

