5.1.6 Adverse Events Associated with Metformin

The potential risks involved in metformin treatment are minimal but include gastrointestinal side effects, lactic acidosis, hepatotoxicity and hypoglycemia. All patients will have a serum pregnancy test (if of childbearing age) and baseline creatinine and liver enzymes drawn at the time of their enrollment. These labs will be reviewed by the principal investigator, and the patient notified that she has been cleared to take metformin per the inclusion/exclusion criteria. Patients will be contacted weekly during the first 2 weeks of metformin treatment and then every 30 days by the study coordinator to ensure that these women are not experiencing any appreciable side effects.

Hypoglycemia is a rare side effect of metformin in both diabetic and non-diabetic patients. See section 4.4.1 for information on management of hypoglycemia.

Please refer to the agent's package insert for a comprehensive list of adverse events.

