8.3 Data Analysis Plans

An exact test for a single proportion will be used to test the hypothesis that the CR rate at 6 months for the group as a whole is greater than 50%. The CR rates at 6 months for the group as a whole and for the CAH and grade 1 EC patients separately will also be estimated and reported along with exact 95% confidence intervals. Patients who progress at 3 or 6 months will be considered non-responders and will be included in these analyses. Patients who fail to complete 3 months of metformin therapy, for reasons unrelated to disease progression or activity, will not be included. The CR rate at 12 months will also be estimated and the analysis will include all patients who had at least 3 months of metformin therapy.

Patient adherence will be described by the percentage of patients able to adhere to at least 80% of planned metformin doses over the course of treatment. The adherence rate will be estimated and reported along with an exact 95% confidence interval. All patients who initiated treatment on study will be included in this analysis. Adverse events will be described by type and grade using frequency tables.

Changes in Ki-67 from baseline to 6 months will be analyzed using a paired t-test or the Wilcoxon signed-rank test as appropriate. Fisher's exact tests will be used to explore associations between expression (via IHC) of the metformin transporter proteins and key targets of the metformin/mTOR signaling pathway and CR at 6 months. Two-sample t-tests will be used to explore associations between metabolic factors and CR. Correlation coefficients and regression models will be used to explore associations between metabolic factors and metformin concentration levels in tumor tissue. Profiling of metabolites and all associated metabolomic analyses will be conducted by the UNC NORC/Nutrition Research Institute Metabolomics Core.

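### Do the 32 accrued patients still yield 30 evaluable ones when patients are enrolled before the D&C that decides whether metformin starts?

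*Combined protocol and SAP*

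**What the plan says.** Section 8.2 gives the accrual goal: "The goal accrual is 32 patients (16 CAH, 16 EC"). One deduction takes it to the 30 used for power: "Our power calculation and analysis will be based on 30 patients, assuming early discontinuation of 2 participants prior to 3 months of treatment". The synopsis (section 1.1) describes the study as 30 evaluable patients, 15 with CAH and 15 with grade 1 EC.

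On timing, section 4.1 says: "While patients will be enrolled prior to dilation and curettage (D&C) and placement of the LR-IUD". Section 4.2 says that "confirmation of CAH or EC will not be made, and therefore metformin will not be started, until after results of the D&C are read", but it also allows the device to be placed in clinic with no D&C if the provider sees no need for one. Section 5.1.6 has "baseline creatinine and liver enzymes drawn at the time of their enrollment".

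On the analysis set, section 6.9 requires at least 3 months of metformin for the primary endpoint, and section 8.3 says: "Patients who fail to complete 3 months of metformin therapy, for reasons unrelated to disease progression or activity, will not be included". The toxicity boundary in section 8.2 counts "patients who have been followed for toxicity for 3 months", and its table has entries up to n = 32.

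**The concern.** The word discontinuation normally implies that treatment had begun. Read that way, the allowance of two covers only patients who start metformin and stop early. A patient who is enrolled, has a D&C and is not confirmed, or who drops out before the first dose, would use one of the 32 places and contribute nothing to the primary analysis. The documents contain no replacement rule and do not say whether the 32 are registered or treated patients.

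At stake would be the power for the primary comparison with 50%. The design has almost no slack at 30: exact power is 80.3% there and below 80% at each of 26 to 29. The observed response rate needed for success also moves, from 70.0% (21/30) to 72.4% (21/29).

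**Working it through.** **Inputs.** From section 8.2: null rate 0.50, alternative 0.75, exact test for one proportion, two-sided alpha 0.05 (upper tail at most 0.025), accrual 32, early losses 2, evaluable 30. The number of non-starters k is not in the documents; 0 to 4 is an assumption used to show the range.

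**Step 1: the plan's own figure.** The cut-off c is the smallest count with P(X ≥ c | n, 0.50) ≤ 0.025, and power is P(X ≥ c | n, 0.75). At n = 30, P(X ≥ 20) = 0.0494 is too large and P(X ≥ 21) = 0.0214 qualifies, so c = 21. Power = P(X ≥ 21 | 30, 0.75) = 0.8034. The stated 80% reproduces.

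**Step 2: add non-starters to both early stops.** Evaluable n = 32 − 2 − k. The last column holds the two-sided level at exactly 0.05 by randomising at the boundary count. This is not a proposed analysis; it separates the loss of patients from the discreteness of the test.

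| k | n | c | c/n | attained two-sided alpha | exact power | power at alpha exactly 0.05 |
|---|---|---|---|---|---|---|
| 0 | 30 | 21 | 70.0% | 0.043 | 80.3% | 81.5% |
| 1 | 29 | 21 | 72.4% | 0.024 | 71.3% | 79.7% |
| 2 | 28 | 20 | 71.4% | 0.036 | 75.0% | 78.1% |
| 3 | 27 | 20 | 74.1% | 0.019 | 64.3% | 77.6% |
| 4 | 26 | 19 | 73.1% | 0.029 | 68.5% | 74.6% |

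One non-starter costs 80.3 − 71.3 = 9.0 points on the exact scale but 81.5 − 79.7 = 1.8 points at fixed alpha. Two cost 5.3 and 3.4 points. The exact column is not even monotone: losing a second patient raises power from 71.3% to 75.0%.

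**Step 3: fewer early stops.** With no early stops and no non-starters, n = 32, c = 23 and exact power is 73.7%. With one early stop, n = 31, c = 22 and it is 77.1%. Two non-starters and no early stops give 32 − 2 = 30 and 80.3%. So a non-starter takes the trial below 30 only when the total of non-starters and early stops exceeds two.

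**Step 4: would counting only starters secure 80%?** Suppose all 32 start and each stops early with probability 2/32 (an assumption that matches the plan's expected two). Exactly 30 evaluable then occurs with probability C(32,2)(2/32)²(30/32)³⁰ = 0.28, and exact power averaged over the binomial number of early stops is 75.8%. Redefining the 32 leaves this variation in place.

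**Step 5: how a patient could fail to start.**
- *Laboratory route.* Creatinine and AST/ALT limits are exclusion criteria (3.2.1). The Time and Events Table (6.1) puts both tests in the screening column, section 6.2 draws them at the screening visit, and section 9.3 requires registration before enrolment, with eligibility confirmed before registration for the lead centre's patients. A patient who fails them is mostly a screen failure and not one of the 32.
- *D&C route.* Histologically confirmed CAH or grade 1 EC is already an inclusion criterion (3.1.1), and every patient arrives with a diagnostic biopsy (6.2). The D&C may be omitted (4.2, 6.3). A shift between CAH and grade 1 EC keeps the patient within the study diagnoses. Only a D&C result outside both would stop metformin on histological grounds, and no rate for that is given.

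**The case for a change.** The best argument for a change is that the protocol separates enrolled from treated patients elsewhere. Section 6.8 counts patients with at least one dose for toxicity and section 6.10 counts those who initiate metformin for adherence, while section 8.2 speaks only of accrual. A small non-start rate would also matter if the two early stops are taken as certain. The chance of keeping 30 evaluable is then (1 − q)³²: 52% at q = 2%, 19% at 5% and 3% at 10%, with average exact power of about 76%, 73% and 69%. One sentence would settle it.

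What stands is that section 8.2 does not define who counts toward 32, and that the D&C route and withdrawal before the first dose are possible. What does not stand is the size. The rates q are assumptions, and the percentages treat exactly two early stops as fixed. The average of 76% at q = 2% is no worse than the 75.8% that chance variation in early stopping gives with no non-starters at all. The boundary table is no evidence of error either. Ending at 32 patients followed for 3 months, it fits a reading in which the 32 are treated patients, or it is an upper limit whose last entries may go unused.

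**Conclusion.** No change follows. The plan ties its 80% to 30 evaluable patients, and that figure is right. Nothing in the documents shows that the design will miss 30, because no non-start rate is given, the laboratory route is mostly closed before registration and the D&C route is narrow. The type I error is not at risk, since the exact test holds its level at any number of evaluable patients.

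The remaining gap is whether the 32 are registered patients or patients who start metformin. With the 30-evaluable target stated in both section 1.1 and section 8.2, a study team would ordinarily count starters, or continue accrual until 30 are evaluable, and the analyst would take the cut-off for the number achieved. If 1 to 4 of the first 32 never started, reaching 32 starters would take about 32/(31/32) = 33 to 32/(28/32) = 36.6 enrolments, that is, 1 to 5 more. At the plan's 1 to 2 patients per month this is roughly 0.5 to 5 months. If nobody acted on it and both early stops occurred, one non-starter would cost 9.0 points of exact power, of which 1.8 points remain once the level of the test is held fixed.

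This rests on the assumed range of 0 to 4 non-starters and on the plan's 50% and 75% response rates.
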